 - ii. Cases in which the subject has a solitary or horseshoe kidney
 - iii. Cases in which the subject has more than two masses in the applicable kidney
 - iv. Cases involving a bilateral operation

III. **STUDY ENDPOINTS.** The Primary and Secondary Endpoints are described on **Exhibit A**. For both the Control Cases and the Intervention Cases (as such terms are defined in Section IV below):

- a. All Primary Endpoints (except Total Operative Time) will be measured by review of the video case recording; and
- b. All Secondary Endpoints and Total Operative Time will be measured using data derived from the EHR.

IV. STUDY DURATION, CASES AND STATISTICAL MODEL

a. Study Duration

This study will commence as soon as practicable following IRB approval, and will end on the earlier of (i) the date on which all Intervention Cases have been performed, as more fully detailed below, and the researchers have completed all associated statistical analysis or (ii) March 31, 2019.

b. Intervention Cases

The set of intervention cases ("*Intervention Cases*") will be all operations:

- That meet the criteria set forth in Section II above;
- Are performed by the surgeons participating in the study;

- Which occur after commencement of the study, until such time as the calculated number of Intervention Cases (as discussed more fully below) have been completed; and
- Which are identified Intervention Cases as discussed in subsection (d) below.

The calculated number of Intervention Cases is set forth on **Exhibit A**. approach used to calculate such number is detailed in subsection (d) below (Randomization, Blinding and Sample Size Calculation)..

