Interims computations of sample size will be performed to ensure the study maintains 70% power to detect a 10% difference in the primary endpoint with use of the appropriate statistical test. An interim computation will occur when ½ of the cases have completed the protocol. The interim computations 1) will involve only interim estimates of standard deviations of interest along with their corresponding 95% confidence intervals, 2) will be blind to whether “Group 1” or “Group 2” was to the VR-aided method, and 3) will not reveal to the surgeons or patients any information about magnitudes of group differences. If power is deemed inadequate, the sample size will be adjusted in both the number of Control Cases and Intervention Cases accordingly. This will be accomplished by repeating the sample size calculation described in Section IVd with data from the ongoing study. Adjustments to sample size are anticipated to be relatively small in relation to the large overall sample size.

c. Control Cases

The set of control cases (“*Control Cases*”) will be all operations:

- That meet the criteria set forth in Section II above;
- Are performed by the surgeons participating in the study;
- Which occur after commencement of the study, until such time as the calculated number of Control Cases (as discussed more fully below) have been completed; and
- Which are identified as Control Cases as discussed in subsection (d) below.

Sample size for Intervention Cases has been calculated based on the methodology described above, and Control Case sample size shall be calculated using a 1:1 group ratio.

d. Randomization, blinding, and sample size calculation

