Eligible subjects identified from the medical record will be those who are 1) scheduled to undergo RALPN surgery, 2) willing to consent to the surgery being performed by one of the four surgeons participating in the study, and 3) willing to be assigned by randomization to a preparation method (VR-aided or control). Each case will be assigned to one of the two preparation methods by a randomization procedure that is stratified by surgeon (four separate surgeon-specific randomization schedules.) Each surgeon-specific randomization schedule will be prepared using permuted blocks of size 2; i.e., each 2-patient block will be some permutation of {VR-aided, Control}. Thus, each surgeon’s cases will be randomized in a 1:1 ratio. Use of permuted blocks thus avoids any confounding of preparation method with temporal trends (e.g., trend due to a learning curve.) Approximately 20 sequentially numbered opaque sealed envelopes (SNOSEs) will be prepared for each individual surgeon, each containing the treatment assignment for one case, and will provided to the Research Coordinator. The treatment code will remain concealed inside the envelope until

the moment the case is ready to be prepared. Patients, personnel gathering data from the video review, and statistician will be blinded. Control and intervention groups identifiers will be known only to the research personnel opening the sealed envelope for random group assignment and extracting patient data from the electronic medical record.

We calculated the sample size based on our pilot data of the total operative time, which shows an effect size of 0.44 regarding the difference of total operative time between VR-aided and control groups. We took the within-surgeon correlation to be 0.3. We use data from the most-of-interest variable (aka total operative time). To account for the within-cluster correlation, we adopted the sample size calculation method proposed in [1]. We took three values of within-cluster correction ($\rho = 0.3, 0.5, 0.7$) to consider low/moderate/high levels of within cluster correlation. In order to account for multiple endpoints and some other unpredictable factors, we propose to raise the sample size by 15%. We selected $\rho=0.3$ given the wide variation in case complexity seen in our pilot study, which drastically limited within-cluster clustering. Our target sample size using this method is 78 patients.

	$\rho = 0.3$	$\rho = 0.5$	$\rho = 0.7$
Before adjustment	34	39	47

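### Fixed blocks of 2 within each surgeon let a surgeon who knows the block size deduce at most 37 to 39 of 78 allocations; the likely effect is small, and larger blocks of varying, concealed size reduce it cheaply.

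*Combined protocol and SAP*

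**What the plan says.** Section IV.d of the combined protocol and SAP stratifies randomisation by surgeon, with four separate 1:1 schedules: "Each surgeon-specific randomization schedule will be prepared using permuted blocks of size 2". Each block holds one VR-aided and one control case. The stated reason is: "Use of permuted blocks thus avoids any confounding of preparation method with temporal trends".

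On concealment, the section says "Approximately 20 sequentially numbered opaque sealed envelopes (SNOSEs) will be prepared for each individual surgeon" and gives them to the Research Coordinator. "The treatment code will remain concealed inside the envelope" until the case is ready for preparation. Patients, video reviewers and the statistician are listed as blinded; surgeons are not. The section adds: "Control and intervention groups identifiers will be known only to the research personnel opening the sealed envelope for random group assignment" and for extracting record data.

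Other sections bear on what surgeons know and do:

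- **Knowledge of the arm.** Surgeons review the VR model before each Intervention Case (VI.c.iv), are told when it is ready (VII.c.iii), and use CT or MRI alone in Control Cases (VII.b.i). The post-operative survey follows Intervention Cases only (V.a).
- **Role in entry.** Surgeons oversee consent (VI.c.ii) and identify the cases for which models will be made (VI.c.i). VII.c.i instead has the investigator or coordinator identify those cases from the randomisation result.
- **Limits on choice.** Each case set "will be all operations" meeting the stated criteria (IV.b, IV.c). Assignment is left to randomisation, for controls in these words: "Which are identified as Control Cases as discussed in subsection (d) below".

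**The concern.** In a block of two, the second assignment is the complement of the first. A sealed envelope hides its contents, but not what follows from the previous envelope in the same block. Someone who knows the block size and the first arm needs no envelope to know the second. The first case of each block stays concealed.

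Surgeons are in that position if they know the block size. It is printed in the protocol, and nothing says that it is kept from them. They also have some influence on entry, because eligibility requires willingness to be randomised and they oversee consent. No step ties a patient to an envelope number before it is opened.

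There is something to select on. Section IV.d cites wide variation in case complexity in the pilot. Sections I.c and I.d report that pilot VR cases had a 27% higher average nephrometry score and that surgeons were readier to take on complex tumours with the models. This makes selection by complexity plausible; it does not show that it will happen here.

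The bias could go either way. Easier cases steered to VR would mimic a benefit, and harder ones would hide it.

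**Working it through.** **1. The plan's total.** Section IV.d gives 34 per arm before adjustment (correlation 0.3) and a 15% increase: 34 × 1.15 = 39.1, taken as 39; 39 × 2 = 78. The stated 78 is reproduced.

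**2. Upper limit.** With n_i cases for surgeon i, the deducible count is the sum of floor(n_i/2) over four surgeons. For a total of 78:

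- no odd surgeon totals (such as 20/20/20/18): 39
- two odd totals (20/20/19/19): 38
- four odd totals (19/19/19/21): 37

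A surgeon who guesses at random on the first case of each block is right in 39 + 39 × 0.5 = 58.5 of 78 cases (75%), against 39 by chance.

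**3. Allowing for timing.** Let p be the share of second cases entered before the first arm is known. The deducible number is then about 39(1 − p). The documents do not give p. I assume random arrivals, a lead of 3 to 14 days from entry to the arm being known, and 78/4 = 19.5 cases per surgeon. Then p = 1 − exp(−lead/gap).

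The accrual periods are also assumptions. The end date in IV.a is the earlier of completion, "as more fully detailed below, and the researchers have completed all associated statistical analysis or (ii) March 31, 2019". From the title date (9/12/2017) that is 565 days. From the July 20, 2018 clearance mentioned in Section I.b it is 254 days. An intermediate 365 days is added.

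| Accrual | Gap per surgeon | p at 3 / 7 / 14 days | Deducible of 78 |
|---|---|---|---|
| 565 days | 29.0 days | 0.10 / 0.21 / 0.38 | 35 / 31 / 24 |
| 365 days | 18.7 days | 0.15 / 0.31 / 0.53 | 33 / 27 / 18 |
| 254 days | 13.0 days | 0.21 / 0.42 / 0.66 | 31 / 23 / 13 |

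**4. Effect on an unadjusted test.** Assume that foreseeable cases are steered by 0.2 SD of complexity in each direction, and that complexity correlates with operative time at r = 0.3 to 0.5. Foreseeable cases are a share 0.5(1 − p) of each arm, so the bias is d = 2 × 0.2 × 0.5(1 − p) × r = 0.2(1 − p)r SD. In a normal approximation with 39 per arm, the test statistic shifts by d × sqrt(39/2), tested at two-sided 5%.

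| p | d at r = 0.3 / 0.5 | Type I error |
|---|---|---|
| 0 (limit) | 0.060 / 0.100 | 5.8% / 7.3% |
| 0.10 | 0.054 / 0.090 | 5.7% / 6.8% |
| 0.53 | 0.028 / 0.047 | 5.2% / 5.5% |
| 0.66 | 0.020 / 0.034 | 5.1% / 5.3% |

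**5. Effect on the adjusted model.** Section IV.e plans a mixed model with the Exhibit A covariates, which include nephrometry score and mass size. If these capture a share R² of the complexity steered on (assumed 50 to 75%), the bias is r(1 − R²) × 0.2(1 − p), with residual SD sqrt(1 − r²R²). At R² = 0.5, r = 0.5, p = 0, the bias is 0.050 and the error 5.6%. At R² = 0.75, r = 0.3, p = 1/3, it is 0.010 and 5.0%.

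**6. What larger blocks change.** In simulated 20-case schedules, the observer knows the possible sizes and all past arms. Random blocks of 4 and 6 give certain prediction for about 6% of cases (blocks of 2: 50%) and correct guessing for about 68% (75%). Bias relative to blocks of 2 is 0.12 if only certain cases are steered and 0.74 with best guessing. At p = 0, best guessing gives d = 0.74 × 0.060 = 0.044 to 0.74 × 0.100 = 0.074, so an error of 5.4 to 6.2% against 5.8 to 7.3%. Steering certain cases only gives 5.0%.

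**The case against.** The strongest reply is that the plan already leaves little room to act. Patients are found from the medical record when already scheduled, both case sets are meant to take every qualifying operation, and the envelopes are numbered, opaque and held by the coordinator. To steer, a surgeon would have to time consent or surgery, or depart from the inclusion rule. No passage says that surgeons know the block size. The planned covariate model absorbs part of any steering on measured complexity, and a surgeon who guesses under blocks of 4 and 6 still keeps about 74% of the bias.

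Most of this stands, and it is why the effect is rated small. It does not close the gap. Inclusion still depends on consent that surgeons oversee, a numbered envelope does not fix which patient comes next, and the Wilcoxon comparison in IV.e is unadjusted.

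The defence that blocks of 2 are needed against time trends is weaker. For an assumed drift of 1 SD over 20 cases, the chance arm difference pooled over four surgeons has an SD of about 0.03 with blocks of 4 and 6, instead of 0.01. The standard error is sqrt(2/39) = 0.23 SD.

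A reader might also take the sentence restricting group identifiers to research personnel as proof that surgeons are blinded, or as a flat contradiction. It may refer only to coded labels. Surgeons cannot be blind to a model that they must review, so the sentence needs clarifying, but it does not decide this point.

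**Conclusion.** The point holds as a limited design weakness. Predictability of up to 37 to 39 of 78 allocations follows from the design on two conditions: the surgeon knows the block size, and knows the first arm before the second case is entered. Under the assumed lead times and accrual periods the count is about 13 to 35; a longer lead or shorter accrual would lower it further.

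The likely inflation is small: about 5.2 to 6.8% for an unadjusted test at p = 0.10 to 0.53, less at higher p, with 7.3% reached only at p = 0. The adjusted model stays at about 5.0 to 5.6%. These figures rest on the assumed steering of 0.2 SD, the assumed correlation and the assumed covariate capture, none of which the documents supply.

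A reader might infer that half the allocations will be known in advance, or that the results will be biased towards VR. The documents support neither. They do not say that surgeons know the block size or how far ahead cases are entered, they contain no evidence of steering, and the direction of any bias is open. The case for change is that it is cheap.

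**What to change.** 1. Generate each surgeon's schedule with randomly varying blocks of 4 and 6, and keep the sizes in a restricted file away from surgeons. This reduces the risk but does not remove it.
2. Have the Research Coordinator log eligible scheduled patients in order, record those not consented and why, and irrevocably assign the next envelope number before opening. This limits reordering and makes omissions visible; it does not stop a surgeon from timing consent.
3. Name a surgeon-stratified rank-sum (van Elteren) test for the continuous endpoints in IV.e. The plan defines no pairs for the signed rank test, and any block pairs would disappear with larger blocks. Re-check the stated 70% power under this test.

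As supporting clarifications only, reconcile VI.c.i with VII.c.i, and reconcile the IV.d sentence on group identifiers with VI.c and VII.b to VII.c, stating that surgeons are unblinded.

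**Cost.** About 4 × 20 = 80 envelopes to re-print, a log to keep, and an amendment to IV.e. The new schedule itself adds no patients; whether the target of 78 suffices under the named test is for the power check to show. A surgeon's arms may differ by up to 3 cases instead of 1, so at worst 12 instead of 4 over four surgeons. In simulation the 95th percentile of the pooled difference is 4 instead of 2. Control of time trends is slightly looser.

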- a. Training with surgeon users on accessing/using mobile app and VR Models. Each surgeon will be trained either in person or via video call. During the training, the surgeon will be trained how to access the VR models from their mobile phones and how utilize several viewing features such as showing/hiding anatomical parts; zooming in/out on the model; and viewing the model in VR mode.
- b. Kickoff Meeting (in-person meeting at medical center):
 - i. Introduce participants
 - ii. Outline study processes, timeline and objectives
- c. Bi-Weekly Assessments
 - i. Data for cases involving the VR Models will be reviewed in a bi-weekly basis to assess whether there are any more or different issues in cases in which the VR Models were used during preoperative planning and, if so, whether any such differences can be attributed to the VR Models.
 - ii. In the event any unexpected adverse event occurs in a case in which a VR Model is used, the study will be immediately suspended until a determination is made whether such event is attributable to the VR Model. If such determination is affirmative, then the researchers will assess whether to continue or discontinue the study based on a number of factors including but not limited to the magnitude of the adverse event, the feasibility of preventative measures, and the likelihood of its recurrence after implementation of any such measures.
- d. Surgeon Experience Surveys (2x during study per surgeon)
- e. Study Conclusion Meeting (in-person): Final study results

EXHIBIT A
COVARIATES, ENDPOINTS AND SAMPLE SIZE BY SURGERY TYPE

		Robotic Assisted Laparoscopic Partial Nephrectomy
Surgical Covariates		
	Unit	
Surgeon Experience Level	Years	✓
Surgeon Identifier	Number	✓
Resident Involvement	Yes/No	✓
Fellow Involvement	Yes/No	✓
Clinical Covariates		
	Unit	
Age	Years	✓
Sex	M/F	✓
Charlson Comorbidity Index	NA	✓
Nephrometry Score	NA	✓
Mass Size	CM	✓
Mass Location	Segment	
Laterality	R/L	✓
Primary Endpoints		
	Unit	
Hilum Dissection	Minutes	✓
Hepatic Vessel Dissection	Minutes	
Tumor Localization	Minutes	✓
Tumor Resection	Minutes	✓
Reconstruction Time	Minutes	✓
Total Operative Time	Minutes	✓
Secondary Endpoints		
	Unit	
Blood Loss	cc	✓
Clamp Time	Minutes	✓
Warm Ischemia Time	Minutes	
Pringle Time	Minutes	
Conversion to Open	Yes/No	✓
Conversion to Radical	Yes/No	✓
Conversion from Wedge to Glissonian	Yes/No	
Intraoperative Complication	Yes/No	✓
Mortality	Yes/No	✓
Patient Hospital Stay	Days (post-op)	✓
Positive Margin	Yes/No	✓

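### Staff who know the allocation abstract total operative time and every secondary endpoint from the EHR; for complications and the undefined operative-time limits this is an avoidable exposure to bias

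*Combined protocol and SAP*

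**What the plan says.** Section IV.d sets out the blinding in two sentences. The first lists who is masked: "Patients, personnel gathering data from the video review, and statistician will be blinded". The second says that the group identifiers are "known only to the research personnel opening the sealed envelope for random group assignment and extracting patient data from the electronic medical record". People who extract EHR data are thus absent from the masked list and present on the list of those who know the arm.

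Section III divides the endpoints by source. Under III.a, "All Primary Endpoints (except Total Operative Time) will be measured by review of the video case recording". Under III.b, "All Secondary Endpoints and Total Operative Time will be measured using data derived from the EHR".

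Section IV.d also shows which endpoint carries most weight: "We calculated the sample size based on our pilot data of the total operative time", and "We use data from the most-of-interest variable (aka total operative time".

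Three other places bear on who does the work. The envelopes go to the Research Coordinator (IV.d). Section VI.b makes that same person responsible for collecting case data in both groups and for making sure that the VR model is looked at before surgery. Section VII.d.ii bars only the principal investigator from entering EMR data. No section provides for a masked EHR abstractor.

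**The concern.** The plan accepts the case for masked data collection, since it masks the video reviewers and the statistician. It does not extend this to EHR abstraction, which supplies the sizing endpoint and every secondary endpoint. A masked statistician cannot correct a difference that entered when the data were abstracted.

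The risk arises where the abstractor must decide something. Exhibit A records intraoperative and post-operative complications as Yes/No, and the documents give no definition, grading or time window. They also do not say when total operative time starts or stops. Someone who knows the arm would be settling borderline events and choosing between candidate times. At stake are the reported complication rates and, if the time limits stay open, the comparison that the trial is sized to make.

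**Working it through.** **1. Count the endpoints.** The inputs are the rows of Exhibit A ticked for partial nephrectomy, the only case type in Section II.

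- Primary, 5 ticked: hilum dissection, tumor localization, tumor resection, reconstruction time, total operative time. Hepatic vessel dissection is not ticked.
- Secondary, 10 ticked: blood loss, clamp time, conversion to open, conversion to radical, intraoperative complication, mortality, hospital stay, positive margin, post-operative complications, readmissions. Warm ischemia time, Pringle time and wedge-to-Glissonian conversion are not ticked.
- Total: 5 + 10 = 15.

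**2. Assign each to its source (Section III).**

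- Video: 5 − 1 = 4 primary endpoints.
- EHR: 10 secondary + total operative time = 11.

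**3. Match the source to the blinding (Section IV.d).**

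| Source | Abstractor knows the arm? | Endpoints |
|---|---|---|
| Video | No | 4 of 15 |
| EHR | Yes | 11 of 15 (11/15 = 73.3%) |

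The second sentence in Section IV.d can describe one group doing both tasks or two groups doing one each. The Research Coordinator's duties favor one group. The table is the same on either reading, because in both the extractors know the arm.

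**4. Sort the 11 by how much the abstractor can decide.** This is a judgement from the units and definitions that the documents give.

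- Little room (8): mortality, conversion to open, conversion to radical, hospital stay, positive margin, readmissions, clamp time, and blood loss (a value in cc that is copied from the record).
- Material room (3): intraoperative complication, post-operative complications, and total operative time for as long as its start and stop are undefined.

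**5. Size of one discretionary call.** The planned size is 39 per arm (Exhibit A; 2 × 39 = 78 in Section IV.d).

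- One call: 1/39 = 2.6 percentage points on that arm's complication rate.
- Two calls: 2/39 = 5.1 points.

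Section IV.e plans Fisher's exact test for binary outcomes. Two-sided p-values for a two-case difference at 39 per arm are:

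- 0 v 2: p = 0.49
- 2 v 4: p = 0.67
- 4 v 6: p = 0.74

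Two calls would visibly shift the reported rates, but a two-case difference would not produce a significant test in these examples. The documents do not say how many calls would be borderline, so this is the effect of a single call and not an estimate of bias.

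**The case against.** The strongest reply is that the count of 11 says little about harm. Most of these items are facts or numbers in the record, and an abstractor who copies them has little to bias. Blood loss may look like a judgement item, but any judgement is the operating team's. The surgeons must know the arm because they view the VR model, so a masked abstractor changes nothing there. If total operative time is read from time stamps, its risk is also small. The other four primary endpoints are timed by masked reviewers, the statistician is masked, and complications are secondary.

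All of this stands, and it limits the point to about three items. It does not remove the point: complications are undefined Yes/No calls, and Section III.b says only that total operative time comes from EHR-derived data, without naming time stamps.

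A second objection concerns the remedy. Handing EHR abstraction to the video reviewers could expose them to operative notes that mention VR, and so unblind the people who time four of the five primary endpoints. This is correct and shapes the fix below.

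A third is that the plan already helps: the outcomes form is keyed to a unique identifier (VII.a), Exhibit C's example fields show no arm, and the principal investigator does not enter EMR data (VII.d.ii). These are partial safeguards. None masks an abstractor who opened the envelope or arranged the VR viewing.

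**Conclusion.** The point holds as a cheap improvement. As written, 11 of the 15 ticked endpoints, including the sizing endpoint, are abstracted by people who know the arm. Material abstractor discretion is confined mainly to intraoperative complication, post-operative complications and the undefined limits of total operative time. The count rests on the ticked rows of Exhibit A and on reading Section IV.d literally. The narrowing to three items rests on the remaining eight being plainly recorded in the EHR.

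A reader might infer more than the documents support:

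- That 11 endpoints, or all safety outcomes, are biased. Nothing shows that any call would be misclassified, and mortality, readmission and similar items leave little to decide.
- That one person certainly both opens envelopes and abstracts data. This is the likelier reading, but it is an inference, and the point does not need it.
- That masking the abstractor would give unbiased EHR outcomes. It would not, because the surgeons know the arm and any influence on what they record stays in the record.

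**What to change.** Make four changes.

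1. In Section IV.d, state that nobody who opens envelopes or coordinates VR viewing abstracts EHR outcomes, and align the Research Coordinator's duties in Section VI.b.
2. Assign abstraction to an existing researcher who opens no envelopes. Use the video reviewers only after all their video timings have been entered and locked; Section VII.d.iii already provides REDCap locking.
3. Give the abstractor a form without the arm and without the Post-Operative Survey fields. Those surveys exist only for Intervention Cases (Section V.a), so a filled survey field reveals the allocation. Finding the EHR record will ordinarily need the medical record number; the linking form in Section VII.a.i holds it and lists no arm field.
4. In Section III.b, name the EHR time stamps that start and stop total operative time.

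The cost is a re-assignment of tasks among research staff and a few sentences of text. The documents give no staffing numbers, so it is an assumption that a suitable researcher is available. Masking will be imperfect if an operative note mentions VR, and bias already in the surgical record will remain.

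### At an effect size of 0.44, 39 patients per arm gives about 59% to 63% power by surgeon (two-sided 0.05, total SD, ρ=0.3), not 70%, and the sample size table does not fit unpaired patients randomised within surgeon

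*Combined protocol and SAP*

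**What the plan says.** All references are to the combined protocol and SAP.

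- **IV.d, effect size.** The basis is pilot data on total operative time, "which shows an effect size of 0.44 regarding the difference of total operative time between VR-aided and control groups".
- **IV.d, correlation.** "We took the within-surgeon correlation to be 0.3"; 0.5 and 0.7 are also tabulated.
- **IV.d, allocation.** Each case is assigned by "a randomization procedure that is stratified by surgeon", in a 1:1 ratio with permuted blocks of 2 for each of four surgeons.
- **IV.d, table.** The numbers before adjustment are 34, 39 and 47 for ρ = 0.3, 0.5 and 0.7; after it they are 39, 45 and 54. The reason for the increase is "In order to account for multiple endpoints and some other unpredictable factors, we propose to raise the sample size by 15" per cent.
- **IV.d and Exhibit A, total.** "Our target sample size using this method is 78 patients". Exhibit A gives 39 Intervention Cases, so 39 is the number per arm.
- **IV.b, power.** The interim computation is to ensure that "the study maintains 70% power to detect a 10% difference in the primary endpoint". Any adjustment is made by "repeating the sample size calculation described in Section IVd with data from the ongoing study", and the interim "will involve only interim estimates of standard deviations of interest" with their confidence intervals.
- **IV.e, test.** The Wilcoxon signed rank test is named both for sizing (again 70% for a 10% difference) and for comparing continuous outcomes. The rejection threshold is 0.05 with no sidedness given. Benjamini-Hochberg control at 5% applies. A mixed model with Exhibit A covariates and random surgeon effects is also planned.

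IV.d itself states no power, sidedness or formula, and does not say which SD standardises 0.44.

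**The concern.** The signed rank test is a one-sample test on paired differences. This trial compares different patients, individually randomised within surgeon, and defines no pairs for analysis. For a standardised difference of 0.44, a two-group comparison needs about twice as many patients per arm as a paired comparison needs pairs. A figure of 34 looks like the paired number.

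The direction of the table adds to the doubt. When both arms sit inside every surgeon, surgeon-to-surgeon variation cancels from the comparison. A higher within-surgeon correlation should then reduce the required number or leave it unchanged. The table goes up.

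The trial may therefore miss a true effect of 0.44 more often than the 3 in 10 that 70% power implies. The interim check would repeat the same calculation and could judge power adequate when it is not.

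**Working it through.** **Inputs from the plan.** Effect size 0.44, ρ = 0.3 (also 0.5 and 0.7), 34 and 39 per arm, 15% uplift (IV.d); 70% power (IV.b, IV.e); threshold 0.05 (IV.e).

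**Assumptions.** Two-sided test; 0.44 on the total SD, with the within-surgeon SD as the alternative; normal data.

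**1. The plan's own figures.** 34, 39 and 47 times 1.15 are 39.1, 44.85 and 54.05, i.e. 39, 45 and 54; 2 × 39 = 78. The uplift and the total are correct.

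For the row before uplift, the one-sample (paired) number is (1.960 + 0.524)² / 0.44² = 31.88. Multiplied by (1 + ρ²) it gives 34.75, 39.85 and 47.50, which rounded down are the three printed entries. The factor (1 + ρ²) is inferred; the plan does not state it. The fit is not unique: one-sided 0.05 with 80% power has base 31.93 and gives 34.81, 39.92 and 47.58, the same row.

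**2. Required number per arm for unpaired patients, 70% power.**

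- Independent patients: 2 × 31.88 = 63.8.
- By surgeon, total SD: 63.76 × (1 − ρ) = 44.6, 31.9, 19.1, so about 45/32/20. This falls with ρ.
- By surgeon, within-surgeon SD: 63.8 at every ρ.
- Ignoring surgeon, within-surgeon SD: 2(1.960/√(1 − ρ) + 0.524)² / 0.44² = 84.9, 112.2, 173.9. This rises with ρ, but far above the printed row.

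**3. Power at 39 per arm.** For t-tests, the noncentrality is (0.44/σ)√(39/2).

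- Independent patients: σ = 1, noncentrality 1.943, 76 df: 48.3%.
- Surgeon-adjusted, total SD, ρ = 0.3: σ = √0.7, standardised effect 0.526, noncentrality 2.322, 73 df: 63.0%.
- Two-patient blocks treated as pairs, total SD, ρ = 0.3: SD of the difference √1.4, standardised 0.372, 39 pairs: 61.9% by paired t.

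Rank tests, and t ignoring surgeon at ρ = 0.3, were simulated (four surgeons with 10, 10, 10 and 9 blocks).

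| Analysis, ρ = 0.3, two-sided 0.05 | 0.44 on total SD | 0.44 on within-surgeon SD |
|---|---|---|
| Rank-sum, ignoring surgeon | 49% | 36% |
| t, ignoring surgeon | 52% | 38% |
| Signed rank on blocks | 60% | 46% |
| Surgeon-stratified rank-sum (van Elteren) | 59% | 45% |
| Surgeon-adjusted t | 63% | 48% to 49% |

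Before the uplift (34 per arm, total SD, ρ = 0.3), surgeon-adjusted t gives 57% and stratified rank-sum 53%.

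**4. Multiplicity.** Exhibit A ticks five primary endpoints for this operation. If total operative time is the only one affected, its Benjamini-Hochberg threshold is near 0.05/5 = 0.01. At that level surgeon-adjusted t (total SD) has about 38% power.

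**5. What reaches 70%.**

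- A one-sided test by surgeon, total SD: 74% at 39 per arm.
- 0.44 as a standardised paired difference: 70.2% at 34 pairs and 76.4% at 39 by paired t.
- Covariates explaining 5%, 15% or 25% of residual variance (an assumed range), with surgeon adjustment on the total SD: 65%, 70% or 75%.
- ρ of 0.5 or 0.7 with surgeon-adjusted t, total SD: 77% or 94%. IV.d selects 0.3.

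**6. The 10% difference.** It equals 0.44 only if the SD is 0.10/0.44 = 22.7% of the mean. The plan prints neither mean nor SD.

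**The case against.** The strongest reply is that the plan never attaches 70% to 0.44. IV.d states no power, and IV.b and IV.e attach it to a 10% difference. The hypothesis in section I.b is directional, so a one-sided test is conceivable. The mixed model is a planned analysis, its covariates include nephrometry score and mass size, and IV.d remarks on wide variation in case complexity. Some explained variance is plausible, and about 15% would be enough. The blocks of 2 also put one VR-aided and one control case under the same surgeon.

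Much of this stands as a limit on certainty. The shortfall depends on a two-sided test, on how 0.44 was standardised and on an unstated covariate contribution. The link from 70% to IV.d rests on the IV.b cross-reference. But the plan commits to neither a one-sided test nor a paired effect size, and gives no figure for variance explained. IV.d describes 0.44 as a difference between groups. Treating the blocks as pairs yields only about 60% to 62% on the total SD.

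A reader might infer that the sponsor demonstrably used a paired formula. The documents do not show that: the fit in step 1 is inferred and not unique, and the method is only cited. A reader might also infer that the trial must grow, or that the interim target must fall below 70%. Neither follows; both are design choices for the sponsor.

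**Conclusion.** The concern holds in this form: the plan's sample size and its only power figure do not agree for the design it describes. With two-sided 0.05, 0.44 on the total SD and ρ = 0.3, an unpaired analysis by surgeon has 59% to 63% power. A true effect of 0.44 would be missed in about 4 trials in 10, or about 5 in 10 if surgeon is ignored. On the within-surgeon SD, power by surgeon is 45% to 49%. Benjamini-Hochberg control can lower these figures.

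The rise of the table with ρ is evidence against it that does not depend on guessing the formula. No reading tried here with unpaired patients gives both the direction and the size of the printed row. It would be too strong to say that power is below 70% on every reading; step 5 gives the exceptions. The 48% for independent patients should not be quoted as a ρ = 0.3 result.

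**What to change.** - **IV.e.** Replace the signed rank test, for both sizing and comparison, with one named unpaired, surgeon-stratified test, for example van Elteren or a surgeon-adjusted linear model.
- **IV.d, inputs.** State the sidedness, the mean and SD in minutes behind 0.44, whether that SD is total or within-surgeon, what ρ means, and the formula.
- **IV.d, table and power.** Replace the table with one for patients randomised within surgeon. Keep 78 patients and say that 39 per arm includes the 15% uplift. Restate the power for the named test: about 59% to 63% on the total SD at ρ = 0.3, or about 45% to 49% on the within-surgeon SD. Note that it is before Benjamini-Hochberg control.
- **IV.b.** Run the interim computation with the corrected unpaired formula and a target difference in minutes fixed beforehand. Whether 70% remains the interim target is for the sponsor to decide.

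The cost is wording in three sections and a less favourable stated power, with no extra patients from the correction itself. If the sponsor keeps 70% at the interim, the existing IV.b rule may then call for more.
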